5.2. Protocol Deviations

Protocol deviations will be documented by the clinical monitor throughout the course of monitoring visits.

The number and percentage of the patients with each major protocol deviation type will be provided for the safety set by treatment arm and dose cohort of mRNA-2416 (as specified in [Section 3.3](#)), total for each treatment arm combining Phase I and Phase II, and overall of Arm A and Arm B. All protocol deviation data will be provided in a listing.

5.3. COVID-19 Impact

A listing will be provided for the impact of coronavirus disease 2019 (COVID-19) on the execution of the study.

6. Demographics and Baseline Characteristics

Demographics and baseline characteristics, as well as baseline disease characteristics, will be summarized using the safety set. Unless otherwise specified, summaries will be presented by treatment arm and dose cohort of mRNA-2416 (as specified in [Section 3.3](#)), total for each treatment arm combining Phase I and Phase II, and overall of Arm A and Arm B.

6.1. Demographics and Baseline Characteristics

Summary statistics will be provided descriptively for the following continuous variables:

- Age
- Baseline weight (kg)
- Baseline height (cm)
- Baseline body mass index (BMI) (kg/m²)

Age will be calculated as the number of months between the birth date and the date of informed consent divided by 12. If the month of the birth date is the same as the informed consent date and the day of the birth date is greater than the date of informed consent, then the age calculated previously should minus 1.

BMI will be calculated as follows:

$$\text{BMI} = \text{weight (kg)} / [\text{height (m)}]^2.$$

The number and percentage of patients will be provided for the following categorical variables:

- Sex (Male, Female with or without childbearing potential)
- Race (American Indian or Alaska Native, Asian, Black or African American, Native Hawaiian or Other Pacific Islander, White, Multiple, Other, Not Reported)
- Ethnicity (Hispanic or Latino, Not Hispanic or Latino)

Demographics and baseline characteristics data will be presented in a listing.

6.2. Baseline Disease Characteristics

Baseline disease characteristics and disease history will be summarized including, but not limited to, the following categories:

- Type of tumor
- Eastern Cooperative Oncology Group (ECOG) performance status (0, 1, 2, 3, 4, 5)
- If solid tumor (Phase I):
 - Solid tumor diagnosis (eg, adrenal, anal, bladder, brain, breast, etc)
 - Time from initial solid tumor diagnosis to first dose of study drug (months)
 - Stage at initial diagnosis (I, II, III, IV)
 - Mutational status (ALK, EGFR, BRAF, BRCA, KRAS, P53, V600, Other)
 - Amplifications (HER2+, MET, Other)
- If solid tumor (Phase II):
 - Solid tumor diagnosis (eg, adrenal, anal, bladder, brain, breast, etc)
 - Time from initial solid tumor diagnosis to first dose of study drug (months)
 - Stage at initial diagnosis (I, II, III, IV)
 - Microsatellite instability (high, intermediate, low, other)
 - Homologous recombination deficiency (positive, negative, other)
 - Tumor mutational burden (high, low, other)
 - Human papillomavirus (positive, negative, other)
 - Estrogen receptor (positive, negative, other)
 - Progesterone receptor (positive, negative, other)
 - HER2/NEU/ERBB2 (positive, negative, other)
- If lymphoma:

- Lymphoma type (Hodgkin lymphoma, Non-Hodgkin lymphoma B-cell lymphoma, Non-Hodgkin lymphoma T-cell lymphoma)
- Lymphoma diagnosis
- Time from initial lymphoma diagnosis to first dose of study drug

Time from initial diagnosis to first dose in months will be calculated as: (Date of first dose - date of initial diagnosis + 1)/30.4375. If the day of initial diagnosis is missing, it will be imputed as the first day of that month. If the day and month of initial diagnosis are missing, it will be imputed as the first day of that year. If all day, month, and year are missing then set to the day before the first dose date.

All disease-specific history data will be presented in a listing.

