 - a. Dose Escalation and Dose Confirmation Periods: Histologically- or cytologically-confirmed advanced/metastatic solid tumor or lymphoma by pathology report and who has received, or been intolerant to, all approved therapies. Advanced solid tumors (i.e. including but not limited to melanoma, breast, head and neck squamous cell) and lymphomas (i.e. including by not limited to diffuse large B cell lymphoma) of any type are eligible for enrollment.
 - b. Dose Expansion Period: Histologically or cytologically confirmed diagnosis of: epithelial cancer of the ovary, fallopian tube, or peritoneum which is platinum resistant or platinum refractory. Patients must have received at least 2 prior lines of therapy. Patients with known BRCA mutation positive must have been treated with and progressed on at least 1 prior PARPi (poly(ADP-ribose) polymerase inhibitor)
3. No limit to the number of prior therapies
 - a. Patients who refuse standard treatments may also be considered provided that he/she has been made aware of all therapeutic options and it is documented in the study records.
4. Lesions for intratumoral injection and biopsies:
 - a. Dose Escalation: A minimum of one lesion that is easily accessible for injection where easily accessible is defined as a cutaneous or subcutaneous mass that is palpable and/or visualizable by ultrasound
 - b. Dose Confirmation: A minimum of one visceral lesion injectable with ultrasound or computer tomography (CT) guidance and that is not encasing or abutting major vascular structures or are in a location that are considered high risk for AEs by the enrolling physician
 - c. Dose Expansion: A minimum of one lesion amenable to injection (either non-visceral or visceral). Patients must have a tumor lesion amenable to biopsy and consent to a pre-treatment and an on-treatment biopsy. For patients with only one lesion amenable to injection, biopsy, and RECIST assessment, the lesion must be ≥ 2 cm.
 - d. Biopsy Cohort Enrichment: Patients must have a tumor lesion amenable to biopsy and consent to a pre-treatment and an on-treatment biopsy
5. All lesion(s) targeted for the initial injection must be ≥ 0.5 cm on longest diameter, be at least 5 mm thick, and have distinct borders based on exam or imaging, not close to critical structures such as major vessels, nerves, or airways
6. Patients must have measurable disease as determined by RECIST v1.1 (solid tumors) or Cheson 2014 criteria (lymphomas).

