Unless otherwise specified, the first/last dose refers to the first/last dose of study drug (mRNA-2416 or durvalumab). Study day for events on or after the date of the first dose will be defined as the number of days from the date of the first dose, plus 1 day, so that the date of the first dose will be defined as Day 1. For events before the date of the first dose, study day will be calculated as the difference in days between the date of the first dose and the date of interest. Thus, the day before the date of the first dose will be defined as Day -1. This means there will be no study Day 0.

Baseline is defined as the last assessment prior to the first dose. All baseline measurements must have been collected prior to administration of the first dose. Measurements obtained after the first dose will be considered as post-baseline values. If the measurement of a variable is not made on a given patient prior to the first dose, that patient will be considered not to have a baseline value for that variable. Change from baseline is defined as post-baseline assessment minus baseline assessment.

Continuous data will be described using the following descriptive statistics: the number of patients (n), mean, standard deviation, median, minimum and maximum, where appropriate. Categorical data will be summarized using the frequency count (n) and percentage (%) of patients for each category, where appropriate. Percentages will be based on non-missing data unless specified otherwise.

Unless otherwise specified, all statistical tests will be 2-sided and conducted at the 0.05 significance level.

No imputation will be applied for missing data unless otherwise specified.

All collected data used for safety and efficacy evaluations will be presented in listings. Data will be displayed in all listings sorted by treatment arm, cohort (dose escalation/confirmation/expansion), dose cohort, and patient identifier unless otherwise specified.

The Medical Dictionary for Regulatory Activities (MedDRA) will be used for coding AEs and medical histories. Prior or concomitant medication data will be coded using the World Health Organization (WHO) Drug Dictionary.

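### A fully missing diagnosis date would be imputed as the day before first dose, giving 0.07 months since diagnosis, which is false for expansion patients and implausible for nearly all others

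*SAP*

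**What the plan says.** SAP Section 6.2 defines time since initial diagnosis, in months, as (first dose date − diagnosis date + 1)/30.4375. It is summarised for solid tumours in both phases, and a corresponding time is listed for lymphoma. Three rules cover incomplete diagnosis dates:

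- Day missing: "If the day of initial diagnosis is missing, it will be imputed as the first day of that month".
- Day and month missing: "If the day and month of initial diagnosis are missing, it will be imputed as the first day of that year".
- Nothing known: "If all day, month, and year are missing then set to the day before the first dose date".

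Under SAP Section 6, demographics "as well as baseline disease characteristics, will be summarized using the safety set", by treatment arm and mRNA-2416 dose cohort, with arm totals and an overall column. The general position in SAP Section 4 is: "No imputation will be applied for missing data unless otherwise specified".

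On prior treatment, Protocol Section 9.1, criterion 2b, requires expansion patients to have platinum-resistant or platinum-refractory epithelial ovarian, fallopian tube or peritoneal cancer, and states: "Patients must have received at least 2 prior lines of therapy". Criterion 2a requires escalation and confirmation patients to have had, or not tolerated, every approved therapy. Criterion 3a lets patients who decline standard treatment be considered. Protocol Section 9.2, criterion 2, excludes anyone given chemotherapy, hormonal or biologic anti-cancer therapy, or non-palliative radiation, within the 14 days before Cycle 1 Day 1.

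**The concern.** A patient about whose diagnosis date nothing is known is given almost the shortest duration the formula can produce. The trial enrols heavily pretreated people with advanced disease, so the value is not a neutral placeholder: it describes a patient who could hardly exist in this population. It would enter the summary as though observed, because Section 6.2 provides no count of imputed dates and no flag.

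The three rules also pull in different directions. Where part of the date is known, the SAP picks the earliest compatible date and so lengthens the duration. Where nothing is known, it picks the last day before dosing and shortens it almost to zero. The sign of the error therefore depends on how much of the date was recorded.

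What is at stake is the baseline table's description of disease duration, mainly in the small dose cohorts.

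**Working it through.** The plan states no figure for this rule, so there is none to reproduce. The check applies the SAP formula.

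**1. Value assigned to a fully missing date.** Diagnosis date = first dose date − 1 day, so the duration is (1 + 1)/30.4375 = 2/30.4375 = 0.0657, or 0.07 months.

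**2. Smallest value compatible with the protocol in expansion.** Platinum-resistant or platinum-refractory disease implies previous chemotherapy, to which the 14-day washout applies. Diagnosis therefore lies at least 14 days before first dose: (14 + 1)/30.4375 = 15/30.4375 = 0.49 months. The imputed value is below this floor by a factor of 15/2 = 7.5, and two or more lines of therapy push the realistic value much higher.

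**3. Direction compared with the partial-date rules.**

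- Day missing, set to the first of the month: duration overstated by at most 30/30.4375 = 0.99 months.
- Day and month missing, set to 1 January: overstated by at most 364/30.4375 = 11.96 months (365/30.4375 = 11.99 in a leap year).
- All missing, set to the day before dosing: duration understated by the true duration less 0.07 months.

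**4. Effect on the mean.** With k affected patients out of n, and a true mean T that also holds for the affected patients, the shift is −(k/n) × (T − 0.0657). T is not in the documents; 12 to 60 months is an assumed range. The group sizes are 3 and 6 (the 3+3 cohort sizes in SAP Section 4.1) and 27 (the Arm A expansion evaluable target, used as an example of a larger group).

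| Affected / n | T = 12 | T = 36 | T = 60 | Relative shift |
|---|---|---|---|---|
| 1 of 3 | −3.98 | −11.98 | −19.98 | about −33% |
| 1 of 6 | −1.99 | −5.99 | −9.99 | about −17% |
| 1 of 27 | −0.44 | −1.33 | −2.22 | about −3.7% |

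Shifts are in months. For example, with 1 of 3 and T = 12: (12 − 0.0657)/3 = 3.98.

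**5. Minimum and median.** One affected patient makes the minimum 0.07 in any column containing expansion patients only, and almost certainly in any other. In a group of 3 with two known values a < b, the rule makes the median a; leaving the date missing gives (a + b)/2 from two patients.

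**The case against.** The strongest reply is that the rule may never be used. Date of diagnosis is a collected item of cancer history (Protocol Section 3, footnote 2). Eligibility needs histological or cytological confirmation, and a date with a known year falls under the partial-date rules. With no fully missing date, nothing changes. This stands: a reader might infer that the baseline summary is biased, but the documents support only that it would be if such a date occurs, and they give no count.

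Second, a reader might infer that the rule breaks the SAP's no-imputation default. It does not. Section 4 allows specified exceptions, and Section 6.2 specifies one. The default shows only that leaving the value missing would fit the SAP's general approach, as would its decision not to impute a wholly missing medication stop date (Section 7.1).

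Third, a reader might infer that 0.07 months is impossible for every patient. For escalation and confirmation that goes too far: criterion 2a accepts intolerance, and criterion 3a allows patients who refused standard treatment to be considered, so a few might have little prior therapy. For them the value is implausible rather than excluded. The expansion argument is unaffected.

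Fourth, a dose cohort of 3 is the extreme. In Arm A a cleared level may add up to 9 biopsy patients, and the MTD/RDE level adds at least 3 confirmation patients, so many columns will be larger and the shift smaller. This is why the effect is given as a range.

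Finally, disease history is listed by patient, so an alert reader could spot a value of 0.07. That softens the problem but does not correct the summary statistics.

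**Conclusion.** The point holds, conditionally and at low severity. As written, the rule gives 0.07 months to any patient with a fully missing diagnosis date. That value is false for expansion patients (floor about 0.49 months) and implausible for nearly all escalation and confirmation patients, and its error runs opposite to that of the neighbouring partial-date rules. If one such date occurs, the mean falls by 4 to 20 months for 1 of 3 patients, 2 to 10 months for 1 of 6, and 0.4 to 2.2 months for 1 of 27. These figures rest on the assumed true mean of 12 to 60 months and on the affected patient being typical of the group.

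A reader might infer some consequence for the efficacy or safety conclusions. The documents do not support that: time since diagnosis is descriptive, and neither the endpoints, the DLT rules nor the Simon two-stage decisions use it.

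**What to change.** In SAP Section 6.2, delete the sentence on fully missing dates. In its place, state that a diagnosis date with no known day, month or year is left missing, that the patient is omitted from the time-since-diagnosis statistics, and that both the number with data and the number missing are shown. Mark such patients in the disease history listing. The partial-date rules can stay.

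The cost is a one-sentence SAP change and the matching line in the derivation program. The number of patients with data is already among the standard statistics in SAP Section 4. No other analysis is touched, and if no diagnosis date is fully missing, no result changes.

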6.3. Medical History

6.3.1. General Medical History

All medical history data will be presented in a listing as collected on the electronic case report form (eCRF).

6.3.2. Prior Therapies/Surgeries

Prior systemic therapies will be coded using the WHO Drug dictionary.

Prior radiation therapy, prior systemic therapy, and prior cancer related surgeries will be presented in separate listings.

7. Treatments and Medications

Treatments and medications will be summarized based on the safety set. Descriptive statistics will be calculated for continuous variables and frequency counts and percentages will be applied to categorical variables. No inferential statistical analysis will be performed.

7.1. Prior and Concomitant Medications

All medications taken at any time from the time of informed consent to the last safety follow up visit must be recorded in the patient's eCRF. Any changes in concomitant medications will also be recorded in the patient's eCRF.

Prior medications are defined as medications that ended before the start of first dose. Concomitant medications are defined as medications started before first dose and continued or ended on or after first dose, or started between first dose and last dose date (inclusive) of study drug.

Missing start dates for concomitant medications data will be handled as follows:

- Missing day only:
 - If the month and year are the same as the first dose month and year, then it will be imputed as the date of the first dose.

- If the month and year are prior to the first dose month and year, then it will be imputed as the last day of the collected month.
- If the month and year are after the first dose month and year, then it will be imputed as the first day of the collected month.
- Missing day and month:
 - If the year is the same as the first dose year, then it will be imputed as the date of the first dose.
 - If the year is prior to the year of the first dose, then it will be imputed as December 31st of the collected year.
 - If the year is after the year of the first dose, then it will be imputed as January 1st of the collected year.
- Missing day, month, and year:
 - It will be imputed as the date of the first dose.

Missing stop dates for concomitant medications data will be handled as follows:

- Missing day only:
 - It will be imputed as the last day of the collected month or the death date, whichever is earlier.
- Missing day and month:
 - It will be imputed as December 31st of the collected year or the death date, whichever is earlier.
- Missing day, month, and year:
 - No imputation is needed.

If the imputed start date is after the stop date, then the start date will be imputed as the stop date.

Prior and concomitant medications will be coded using the WHO Drug dictionary. The dictionary will be updated throughout the life of the project to allow for the most recent version of the dictionary to be used.

Prior and concomitant medications will be summarized in separate tables by treatment arm and dose cohort of mRNA-2416 (as specified in [Section 3.3](#)), and total for each treatment arm combining Phase I and Phase II. The number and percentage of patients receiving at least one medication will be presented. In addition, the tables will present the number and percentage of patients by drug class and preferred term. Drug classes will be sorted alphabetically, while preferred terms within each drug class will be presented in descending order of frequency based on the total of Arm B combining Phase I and Phase II. At each level of patient summarization, a patient is counted once if the patient reported one or more medications.

All prior and concomitant medications will be presented in a listing.

7.2. Medical Procedures/Surgeries

Medical procedures/surgeries will be presented in data listings.

7.3. Study Treatments

Study treatments will be summarized by treatment arm and dose cohort (as specified in [Section 3.3](#)) for Phase I and Phase II, and total for each treatment arm combining Phase I and Phase II. Descriptive statistics will be provided in the following categories.

- Arm A: treatment duration, number of dosing cycles, and cumulative dose of mRNA-2416 during the treatment period.
- Arm B: treatment duration, number of dosing cycles, and cumulative dose of mRNA-2416; treatment duration, number of dosing cycles, and cumulative dose of durvalumab during the treatment period (including combination treatment with mRNA-2416 and continuation treatment as a single agent), separately.

All study treatment data will be presented in a listing.

7.3.1. Extent of Exposure

Treatment duration of mRNA-2416 (weeks) is defined as:

$[(\text{last dose date of mRNA-2416}) - (\text{first dose date of mRNA-2416}) + 1]/7$.

Treatment duration of durvalumab (weeks) is defined as:

$[(\text{last dose date of durvalumab}) - (\text{first dose date of durvalumab}) + 1]/7$.

7.3.2. Cumulative Dose

Cumulative dose of mRNA-2416 is defined as the sum of all mRNA-2416 doses (mg) taken during the treatment period. Cumulative dose of durvalumab is defined as the sum of all durvalumab doses (mg) taken during the treatment period.

7.3.3. Number of Dosing Cycles

Number of dosing cycles is defined as the total number of cycles at which the patient received non-zero mRNA-2416 doses. Number of dosing cycles is defined as the total number of cycles at which the patient received non-zero durvalumab doses.

7.3.4. Treatment Modifications

Number of patients with mRNA-2416 injection administered, number of patients without mRNA-2416 injection administered, reason for mRNA-2416 injection not administered, number of patients who had dose modified, categories of dose modification, reason for dose modified, number of lesion injected, and

lesion type will be summarized by scheduled visits, treatment arm and dose cohort for Phase I and Phase II, and total for each treatment arm combining Phase I and Phase II.

Number of patients with durvalumab administered, number of patients without durvalumab administered, action taken with durvalumab, and reason for action on durvalumab will be summarized by scheduled visits and dose cohort for Phase I and Phase II, and total for Arm B combining Phase I and Phase II.

8. Efficacy Analysis

All tables and figures for efficacy evaluations will be conducted using the activity evaluable set by treatment arm and dose cohort (as specified in Section 3.3) for Phase I and Phase II, and total for each treatment arm combining Phase I and Phase II. Listings will be based on the safety set.

Solid tumor response will be assessed by investigators based on RECIST 1.1 (complete response [CR], partial response [PR], stable disease [SD], progressive disease [PD], or not evaluable [NE]), and based on irRC (immune-related complete response [irCR], immune-related partial response [irPR], immune-related stable disease [irSD], immune-related progressive disease [irPD], or not evaluable [NE]). Lymphoma response will also be assessed by investigators based on Cheson 2014 criteria (positron emission tomography [PET]-CT-based complete metabolic response, partial metabolic response, no metabolic response, or progressive metabolic response; CT-based complete radiologic response, partial radiologic response, SD, or PD), and based on LYRIC (PET-CT-based complete metabolic response, partial metabolic response, no metabolic response, progressive metabolic response, or indeterminate response; CT-based complete radiologic response, partial radiologic response, SD, PD, or indeterminate response). Best overall response is determined from time-point overall response. When SD for RECIST 1.1 or irSD for irRC is believed to be the best overall response, it must meet the minimum time (at least 55 days between the first dose date and the last SD assessment date, and no PD between). Death may be considered in determination of best overall response.

Listings will be provided for tumor assessment of target lesions, non-target lesions, new lesions, and overall response evaluation. Waterfall plots of best percent change from baseline in sum of diameters of target lesions based on investigator assessments (per RECIST 1.1 and irRC, respectively) will be provided by treatment arm, and by treatment arm and injection status, respectively.

The following efficacy endpoints will be analyzed:

- ORR based on RECIST 1.1/Cheson 2014 criteria
- ORR based on irRC/LYRIC
- DOR based on RECIST 1.1/Cheson 2014 criteria
- PFS based on RECIST 1.1/Cheson 2014 criteria
- PFS based on irRC/LYRIC
- DCR based on RECIST 1.1

All derived efficacy parameters will be displayed in a data listing.

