APPENDIX C: SUMMARY OF TUMOR ASSESSMENT CRITERIA

Table 1a: Comparison between RECIST 1.1 and irRC

Criteria	CR	PR	PD
RECIST 1.1	Disappearance of all target lesions. Any pathological lymph nodes (whether target or nontarget) must have reduction in short axis to <10 mm	At least a 30% decrease in the sum of diameters of target lesions, taking as reference the baseline sum diameters	At least a 20% increase in the sum of diameters of target lesions, taking as reference the smallest sum on study (this includes the baseline sum if that is the smallest on study). In addition to the relative increase of 20%, the sum must also demonstrate an absolute increase of at least 5 mm
			Note: the appearance of one or more new lesions is also considered progression.
irRC	Disappearance of all lesions in two consecutive observations not less than 4 weeks apart	≥50% decrease in tumor burden compared with baseline in 2 observations at least 4 weeks apart (as measured bi-dimensionally)	≥25% increase in tumor burden compared with nadir (at any single time point) in 2 consecutive observations at least 4 weeks apart, where Tumor Burden = SPD index lesions + SPD new, measurable lesions

Table 1b: Comparison between Cheson Criteria and LYRIC

Criteria	CR	PR	PD

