Cheson (Lugano)	PET-CT, score 1, 2, or 3* with or without a residual mass on 5PS† OR on CT, target nodes/nodal masses must regress to ≤ 1.5 cm in LDi	PET-CT score 4 or 5 with reduced uptake compared with baseline and residual mass(es) of any size. OR On CT $\geq 50\%$ decrease in SPD of up to 6 target measurable nodes and extranodal sites	
PET-CT score 4 or 5 with an increase in intensity of uptake from baseline and/or new FDG-avid foci consistent with lymphoma at interim or end-of-treatment assessment. OR On CT, an individual node/lesion must be abnormal with: LDi > 1.5 cm and increase by $\geq 50\%$ from PPD nadir and an increase in LDi or SDi from nadir 0.5 cm for lesions ≤ 2 cm 1.0 cm for lesions > 2 cm
 
In the setting of splenomegaly, the splenic length must increase by $> 50\%$ of the extent of its prior increase beyond baseline (eg, a 15-cm spleen must increase to > 16 cm). If no prior splenomegaly, must increase by ≥ 2 cm from baseline. New or recurrent splenomegaly
 
New or clear progression of preexisting nonmeasured lesions
 
Regrowth of previously resolved lesions
 
A new node > 1.5 cm in any axis or a new extranodal site > 1.0 cm in any axis; if < 1.0 cm in any axis, its presence must be unequivocal and must be attributable to lymphoma
 
Assessable disease of any size unequivocally attributable to lymphoma
 
AND/OR new or recurrent involvement of the bone marrow

LYRIC	Same as Cheson	Same as Cheson	
As with Lugano with the following exceptions:
 
IR
 
IR(1): $\geq 50\%$ increase in SPD in first 12 weeks
 
IR(2): $< 50\%$ increase in SPD with
 
a. New lesion(s), or
 
b. $\geq 50\%$ increase in PPD of a lesion or set of lesions at any time during treatment
 
IR(3): Increase in FDG uptake without a concomitant increase in lesion size meeting criteria for PD

Reference: Cheson BD, Ansell S, Schwartz L, et al. Refinement of the Lugano Classification lymphoma response criteria in the era of immunomodulatory therapy. *J Clin Oncol.* 2014; 32(27):3059-68

Table 2: Derivation of irRC overall responses

Measurable response	Nonmeasureable response		Overall response
Index and new, measureable lesions (tumor burden),^a %	Non-index lesions	New, nonmeasurable lesions	Using irRC
↓100	Absent	Absent	irCR ^b
↓100	Stable	Absent	irPR ^b
↓100	Unequivocal progression	Absent	irPR ^b
↓≥50	Absent/Stable	Absent	irPR ^b
↓≥50	Unequivocal progression	Absent	irPR ^b

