5PS=5-point scale; CT=computed tomography; FDG=fluorodeoxyglucose; IHC=immunohistochemistry; LD_i=longest transverse diameter of a lesion; MRI=magnetic resonance imaging; PET=positron emission tomography; PPD=cross product of the LD_i and perpendicular diameter; SD_i=shortest axis perpendicular to the LD_i; SPD=sum of the product of the perpendicular diameters for multiple lesions.

Reference:

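### The waterfall plot labelled irRC is specified on the RECIST 1.1 diameter scale and leaves out new measurable lesions, so a bar can disagree with the patient's irRC category

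*SAP*

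**What the plan says.** SAP Section 8 (Efficacy Analysis) asks for waterfall plots of the best percentage change relative to baseline "in sum of diameters of target lesions based on investigator assessments (per RECIST 1.1 and irRC, respectively". One set is by treatment arm; the other is by treatment arm and injection status. The sentence names a single measure and attaches both criteria to it.

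Protocol Appendix C, Table 1a, uses the sum of diameters for RECIST 1.1 only. Partial response there is "At least a 30% decrease in the sum of diameters of target lesions, taking as reference the baseline sum diameters". For irRC the same table gives partial response as "≥50% decrease in tumor burden compared with baseline in 2 observations at least 4 weeks apart (as measured bi-dimensionally" and progression as "≥25% increase in tumor burden compared with nadir (at any single time point) in 2 consecutive observations at least 4 weeks apart", with "Tumor Burden = SPD index lesions + SPD new, measurable lesions". Table 2 of that appendix derives the irRC overall response from a column headed "Index and new, measureable lesions (tumor burden". The abbreviations at the end of Appendix C, given for the lymphoma criteria, define the term: "SPD=sum of the product of the perpendicular diameters for multiple lesions".

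The SAP reports irRC response categories, ORR and PFS, but nowhere gives irRC tumor burden a different definition. SAP Section 13 lists one change to the planned analysis, the omission of a correlation endpoint.

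**The concern.** Two features separate irRC burden from the RECIST 1.1 sum: it is measured in two dimensions, and it counts new measurable lesions. The specified waterfall has neither. A programmer who follows the sentence will produce a figure labelled irRC that shows a different quantity.

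The second feature matters most in this trial. Under RECIST 1.1 a new lesion is progression outright; under irRC a new measurable lesion adds to the burden. Protocol Section 10.10 lets patients continue treatment past RECIST progression until irRC progression is confirmed. An irRC figure that ignores new lesions therefore drops a main reason for showing irRC at all. A patient whose target lesions shrink while a new lesion grows would appear as a clear reduction under an irRC label.

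**Working it through.** The plan states no figure to reproduce. The check sets the definitions side by side and then converts between the two scales.

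**Definitions**

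| | SAP Section 8 waterfall (both criteria) | RECIST 1.1, Appendix C | irRC, Appendix C |
|---|---|---|---|
| Measure | Sum of diameters | Sum of diameters | Sum of products (SPD) |
| Lesions summed | Target | Target | Index plus new measurable |
| Partial response, from baseline | none stated | -30% | -50% |
| Progression, from smallest value | none stated | +20% and at least 5 mm, or a new lesion | +25% |

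The specified measure matches the RECIST column and differs from the irRC column in both of the first two rows.

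**Step 1: no new lesions, uniform change.** Assume both axes of every lesion change by the same fraction d. Then the SPD change is s = (1 + d)² - 1, and d = √(1 + s) - 1.

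- d = -0.30 gives s = 0.70² - 1 = -0.51, so -51%.
- s = -0.50 gives d = √0.50 - 1 = -0.293, so -29.3%.
- s = +0.25 gives d = √1.25 - 1 = +0.118, so +11.8%.
- d = +0.20 gives s = 1.20² - 1 = +0.44, so +44%.

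The partial-response limits almost coincide (-29.3% against -30% in diameter). The progression limits do not (+11.8% against +20%, each from the smallest value).

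**Step 2: no new lesions, unequal change (assumed lesions).** Lesions of 60×60 and 20×20 mm become 50×50 and 5×5 mm.

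- Diameters: 80 to 55 mm, 55/80 - 1 = -31.3%.
- SPD: 3600 + 400 = 4000 to 2500 + 25 = 2525 mm², 2525/4000 - 1 = -36.9%.

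The bar passes -30%, but the irRC burden is short of -50%. The near-coincidence in step 1 depends on uniform change.

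**Step 3: with a new measurable lesion (assumed lesions).** Target lesions of 30×30 and 20×20 mm become 18×18 and 12×12 mm. For simplicity, take one post-baseline assessment, the same lesions as target and index, and the new lesion present at that assessment.

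- Plotted bar: 50 to 30 mm, 30/50 - 1 = -40%.
- SPD of index lesions: 900 + 400 = 1300 to 324 + 144 = 468 mm², 468/1300 - 1 = -64.0%.
- Adding a new 25×25 mm lesion: (468 + 625)/1300 - 1 = -15.9%, in the irSD range.
- Adding a new 35×35 mm lesion: (468 + 1225)/1300 - 1 = +30.2%, in the irPD range if confirmed at least 4 weeks later.

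The bar is -40% in both cases.

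**The case against.** The strongest defence is that the closing word of the SAP sentence may mean each criterion's own measure. That may be the intent, but the text names the sum of diameters of target lesions for both, and a figure is programmed from the text. The clause in SAP Section 1 that gives the SAP precedence over the protocol does not help: applied literally, it fixes a measure that does not match the irRC categories the SAP itself reports.

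A second defence is that any target-lesion waterfall omits new lesions, the RECIST one included, and that the SAP lists new lesions and overall response separately. This is fair. The difference is that the RECIST 1.1 sum excludes new lesions by definition, whereas irRC burden includes new measurable ones. The fault is the irRC label on that measure.

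Three stronger readings are tempting and are not supported:

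- *That the figure contradicts the irRC response in general.* It can disagree in some patients. Without new lesions and with uniform change, the response limits nearly coincide.
- *That the irRC plot merely repeats the RECIST plot.* The documents do not establish this. Appendix C counts irRC lesions above 5 × 5 mm, while Appendix D requires 10 mm on CT, so the lesion sets may differ. Treatment may run past RECIST progression, and the SAP does not state which assessments enter the best change.
- *That irRC results are affected.* SAP Section 8 takes best overall response from investigator time-point responses. ORR follows from best overall response, and PFS from progression or death.

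**Conclusion.** The specification is wrong as written, and the consequence is small. The plot labelled irRC is not on the irRC scale and leaves out new measurable lesions, so a bar can disagree with the irRC category: in the example, -40% against -15.9% or +30.2%. Those sizes rest on assumed lesions and show what is possible. The documents give no basis for saying how often it would happen.

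The reach is one descriptive figure type for an exploratory criterion. The Phase II primary endpoint is response rate by RECIST 1.1 and is untouched, as are irRC ORR and PFS.

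**What to change.** In SAP Section 8, split the sentence in two.

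- RECIST 1.1 waterfall: keep the sum of diameters of target lesions.
- irRC waterfall by treatment arm: plot the best percentage change from baseline in total irRC tumor burden (SPD of index lesions plus SPD of new measurable lesions), with a reference line at -50% only. A line at +25% should not be drawn: irPD is measured from nadir, so it has no fixed position on a change-from-baseline axis.
- Waterfall by injection status: title it as target-lesion diameter change and remove irRC from the label, because the plan gives no rule for assigning a total burden that includes new lesions to injection status.

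The cost is one figure specification and its programming. It depends on perpendicular diameters being in the database. irRC assessment calls for them, but the case report form is not among the documents, so this cannot be confirmed here. If they were not captured, relabel the arm-level plot in the same way and drop irRC from it.
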